#### Part A Multiple Imputation Procedure

Assuming the post-vaccination  $\log_{10}$  neutralizing antibody results are normally distributed, MI will be used to create 100 complete data sets that will account for the random variability in the  $\log_{10}$  neutralizing results. MI sensitivity analyses will only be performed for the Part A cohort(s) formally tested for non-inferiority of ABNCoV2 to Comirnaty, and Cohort 1 and 2 analyses will be performed separately but using the same method. As enrollment in Cohort 1 did not meet the sample size requirement for the formal non-inferiority test, the MI procedure will not be performed for that cohort. Baseline  $\log_{10}$  neutralizing antibody results, Week 1  $\log_{10}$  neutralizing antibody results, race group, sex, age group (<65 years versus  $\geq 65$  years), and prior vaccination regimen will be used in the joint model to predict the  $\log_{10}$  neutralizing antibody value for the primary estimand time point at Week 2.

MI analyses will be performed in SAS using the PROC MI and PROC MIANALYZE procedures, employing a fully conditional specification (FCS) model. A minimum of  $\log_{10}$  of half of the LLOD will be set for imputed values to correspond to the observed data range. In addition, a seed of 19201 will be used for the procedure. Analyses will be performed separately for each cohort in Part A. Sample SAS code is provided in [Appendix 2](#).

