### Primary Estimand

The primary variable of interest is the subjects' neutralizing antibody result against the SARS-CoV-2 index virus measured at 2 weeks after trial vaccination in each Part A cohort, and the variable will be summarized as the ratio of geometric means for ABNCoV2 compared to Comirnaty in subjects meeting the Immunogenicity Analysis Set (IAS) definition.

The planned primary analysis will be conducted in each of the Part A cohorts, and the null hypothesis of inferiority will be rejected if the ratio of GMTs is within the non-inferiority margin of 0.67, i.e., the lower limit of the 2-sided 97.5% CI of the GMT ratio is  $\geq 0.67$ .

The following are considered intercurrent events:

1. Development of COVID-19 symptoms and having a positive test for SARS-CoV-2 infection prior to Visit 3 (12 to 16 days after vaccination) by PCR or other testing method,

2. Administration of a booster for SARS-CoV-2 prior to Visit 3, and
3. Discontinuation from the trial due to AEs.

For the primary estimand, the third intercurrent event is not considered as having an impact on the SARS-CoV-2 neutralizing antibody levels and therefore the “treatment policy” strategy will be used. Exposure to the virus or receiving another booster vaccine can have significant effect on SARS-CoV-2 neutralizing antibody levels, and thus subjects who develop intercurrent infections will be excluded from the primary analysis. This is equivalent to the “while on treatment” strategy. Prior to database lock, a data review meeting will determine if any other intercurrent events (e.g., protocol violations) would affect the primary immunogenicity outcome. Strategies to handle these additional intercurrent events will be determined in a blinded fashion.

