### 4.2.2. Main Analytical Approach

The estimate of the primary estimand will be created using the IAS.

The geometric mean, 95 % CI, median, minimum, and maximum of SARS-CoV-2 neutralizing antibody results for Part A will be calculated within each cohort. Additionally, in Part A, the ratios of the GMTs between ABNCoV2 and Comirnaty will be provided along with p-values, 95% CI and 97.5% CI from a generalized linear model. Age and baseline neutralizing antibody results will be included as covariates in the model to compare between the vaccination arms. The Least Squares (LS) Means and CIs from the model will be back transformed to their original scale.

GMTs will be obtained by computing the arithmetic means and the corresponding 95% CIs on the  $\log_{10}$  scale, and then exponentiating the  $\log_{10}$  means and confidence limits to return the results to the original scale.

Figures of neutralizing antibody results with the GMT and fold increase for the index virus and each VOC will be plotted by cohort, and for both cohorts combined, for each vaccination arm in Part A.

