#### 4.2.3.1. Sensitivity using Multiple Imputation for the Safety Analysis Set

Because the window between vaccination and the primary endpoint measurement is short, the number of subjects with missing data due to intercurrent events or protocol deviations substantially affecting the immunogenicity results is expected to be small. If >5% of data are missing despite the short window, missing values will be imputed via the multiple imputation (MI) method as a sensitivity analysis using the Safety Analysis Set. Missing values will be assumed to be missing at random, such that the reason for the missing value is not dependent on the result itself. As the MI procedure will be performed on the Safety Analysis Set, regardless of protocol deviations, neutralizing antibody results after vaccination that are out of window will be included rather than imputing a “missing” value for full accounting of the available data. Inclusion of serum samples collected out of window will follow the method used for the Sensitivity Analysis using the Safety Analysis Set.

The MI sensitivity analyses will be performed separately for each Part A cohort due to the different background characteristics.

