**Table 10: Immunogenicity Sampling and Analysis by Endpoint**

Endpoint	Part A		Part B	
	Cohort 1	Cohort 2	Cohort 1	Cohort 2
Index Virus Serum Samples Baseline and Week 2	All	All	~250 subjects	~250 subjects
VOCs Serum Samples Baseline and Week 2	All	All	N/A	N/A
Index Virus Serum Samples for Exploratory Timepoints: Weeks 1, 4, 13, and 26	All	~250 subjects	N/A	N/A
VOCs Serum Samples for Exploratory Timepoints: Weeks 1, 4, 13, and 26	All	All	N/A	N/A
ELISA	All	~250 subjects	N/A	N/A
ELISpot	N/A	N/A	All PBMC subset subjects with matching baseline and post baseline visits	All PBMC subset subjects with matching baseline and post baseline visits

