## APPENDIX 2. SAS CODE FOR MULTIPLE IMPUATION SENSITIVITY ANALYSIS

If >5% of Week 2 neutralizing antibody results are missing for Part A, the multiple imputation code will be run separately for both Part A cohorts, with the appropriate values for prior regimen, shown below, included in each model.

At the time of finalization of the statistical analysis plan, enrollment has completed, and Cohort 1 of Part A did not reach the required sample size for the primary analysis. The MI analysis of Cohort 2 of Part A only will be performed if there are >5% of Week 2 neutralizing antibody results missing.

titersl: the dataset containing the log10 neutralizing antibody results data along with the covariates used in the analysis, one record per subject.

- sex: Male vs. Female
- racegroup: White vs. Other
- agegroup: <65 years vs. ≥65 years
- priorreg (categories different by cohort):
  - Cohort 1:
    - 2 doses of mRNA vaccine,
    - 1 dose or 2 doses of adenovirus-based vaccine,
    - 1 dose of adenovirus-based vaccine followed within 3 months by 1 dose of mRNA vaccine,
    - Other authorized primary vaccination regimen.
  - Cohort 2:
    - 2 doses of mRNA primary vaccines plus 1 booster dose of mRNA vaccine,
    - 1 dose or 2 doses of adenovirus-based primary vaccines plus 1 booster dose of mRNA vaccine,
    - Other authorized primary vaccination and boost vaccination combinations.
- ltiterBL: Log10 Baseline Neutralizing Antibody Result
- ltiterW1: Log10 Week 1 Neutralizing Antibody Result
- ltiterW2: Log10 Week 2 Neutralizing Antibody Result

```
proc mi data=titersl out=titermi nimpute=100 seed=19201
        minimum=[log10(LLOD/2)];
class sex racegroup agegroup priorreg;
var sex racegroup agegroup priorreg ltiterBL ltiterW1;
```

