## Statistical Analysis Plan [Final 1.0]

```
      fcs nbiter=20 reg(ltiterW2 = ltiterBL ltiterW1 agegroup priorreg sex
racegroup /details);
run;

proc means data=titermi noprint nway;
  by _imputation_;
  var ltiterW2;
  output out=summ(drop=_type_ _freq_) n=n mean=logmn stderr=logse;
run;

ods output parameterestimates=PartACohort1Est;
proc mianalyze data=summ;
  modeleffects logmn;
  stderr logse;
run;
data PartACohort1Est2;
  set PartACohort1Est;
  GMT=10**estimate;
  GMT_LCL=10**LCLmean;
  GMT_UCL=10**UCLMean;
  keep estimate lclmean uclmean gmt;;
  label estimate='Mean Log10 Titers'
         lclmean='Lower 95% CI of the Mean Log10 nAb Result'
         uclmean='Upper 95% CI of the Mean Log10 nAb Result'
         gmt='Geometric Mean Titer'
         GMT_LCL='Lower 95% CI of the Geometric Mean nAb Result'
         GMT_UCL='Upper 95% CI of the Geometric Mean nAb Result'
run;
```

(Repeat for Part A Cohort 2 if sample size for cohort meets minimum for non-inferiority testing.)

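### The multiple-imputation check omits vaccination arm and pools both vaccines into one GMT, so it cannot test the Cohort 2 non-inferiority result

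*SAP*

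**What the plan says.** The primary estimand (SAP 1.1) is the ratio of geometric means, ABNCoV2 to Comirnaty, at Week 2. Non-inferiority holds if "the lower limit of the 2-sided 97.5% CI of the GMT ratio is" at least 0.67. The model behind that ratio is in SAP 4.2.2: "Age and baseline neutralizing antibody results will be included as covariates in the model to compare between the vaccination arms".

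SAP 4.2.3.1 sets the trigger for imputation: "If >5% of data are missing despite the short window, missing values will be imputed via the multiple imputation (MI) method". It applies only to a Part A cohort that is formally tested. Cohort 1 was under-enrolled, so that leaves Cohort 2. The predictors listed are baseline and Week 1 log10 results, race group, sex, age group "and prior vaccination regimen will be used in the joint model to predict the" Week 2 value.

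In Appendix 2 the variable list is "var sex racegroup agegroup priorreg ltiterBL ltiterW1". The CLASS statement and the FCS regression contain no arm variable either. After imputation, `PROC MEANS` runs by `_imputation_` only, with "output out=summ(drop=_type_ _freq_) n=n mean=logmn stderr=logse". `PROC MIANALYZE` pools that one mean, and its limits carry labels such as "lclmean='Lower 95% CI of the Mean Log10 nAb Result".

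**The concern.** A sensitivity analysis for missing data should re-estimate the primary quantity under a different treatment of the missing values. This one estimates something else. It has two separate faults.

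- **Imputation model.** It leaves out the factor whose effect is being tested. Missing ABNCoV2 and Comirnaty results are then drawn from one common regression.
- **Analysis step.** It returns one GMT averaged over both vaccines. There is no arm contrast, no adjustment for age or baseline, and no 97.5% limit.

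The first fault would outlast a repair of the second. If someone added an arm comparison to these imputed datasets, the ratio would be drawn toward 1. At a true ratio below 1 that favors non-inferiority, which is the wrong direction for a robustness check.

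**Working it through.** **1. The test being checked.** Inputs from SAP 5.1 are SD 0.52 (log10), margin 0.67, one-sided α 0.0125 and 450 evaluable subjects (225 per arm at 1:1). A true ratio of 1 is assumed.
- Margin on the log10 scale: −log10(0.67) = 0.1739.
- SE = 0.52 × √(2/225) = 0.0490.
- Power = Φ(0.1739/0.0490 − 2.241) = 90.4%. The plan says about 90%.
- With 200 per arm, power is 86.5%. The plan says about 86%.

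The plan's own figures reproduce.

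**2. What the code can return.** The only pooled parameter is the overall log10 mean, so no between-arm contrast can be recovered from the output. The confidence level also differs from the decision rule, 1.960 against 2.241 standard errors. At a ratio of 1 with 225 per arm, the lower limit would be 10^(−1.960 × 0.0490) = 0.802 at 95% and 10^(−2.241 × 0.0490) = 0.776 at 97.5%.

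**3. Bias if a ratio were derived anyway.** Suppose a fraction f is missing completely at random in each arm and there is no Week 1 information. Imputed subjects then contribute no arm difference on average, so the log ratio shrinks by the factor (1 − f):
- f = 0.06: 0.67^0.94 = 0.686
- f = 0.10: 0.67^0.90 = 0.697
- A true ratio of 1.00 stays 1.00.
- A true ratio of 1.25 becomes 1.25^0.90 = 1.22.

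**4. Simulated error rate at a true ratio of 0.67.** The setup was 250 per arm, SD 0.52, 20 imputations, Rubin's rules, an analysis model of arm plus baseline, and a two-sided 97.5% CI. The following are assumptions, not document values: data missing completely at random, baseline–Week 2 correlation r from 0.2 to 0.6, Week 1–Week 2 correlation 0.8, and a Week 1 arm effect of 50% or 100% of the Week 2 effect.

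| Imputation model | Missing | Week 1 data | Mean ratio | One-sided error |
|---|---|---|---|---|
| Arm omitted | 6% | none | 0.687 | 0.014–0.018 |
| Arm omitted | 10% | none | 0.698 | 0.018 / 0.020 / 0.023 at r = 0.2 / 0.4 / 0.6 |
| Arm omitted | 10% | 250 of 500, 50% effect, r = 0.4 | 0.692 | 0.019 |
| Arm omitted | 10% | 250 of 500, 100% effect, r = 0.4 | 0.686 | 0.015 |
| Arm included | 10% | none | 0.671 | 0.012 |
| Arm included | 10% | 250 of 500 | 0.670 | 0.013 |

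At 10% missing, Monte Carlo error is ±0.002 with arm omitted and no Week 1 data (20,000 trials), ±0.003 with arm omitted and half Week 1 data (8,000 trials), and ±0.0015 and ±0.0035 for the two arm-included rows.

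A separate run of 3,000 trials at r = 0.5, with arm omitted, 10% missing and no Week 1 data, gave an error of 0.028. Its Monte Carlo margin is 1.96 × √(0.028 × 0.972/3000) = ±0.006, so it is compatible with the table.

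**5. Can Week 1 stand in for arm?** Only in part. The row "Index Virus Serum Samples for Exploratory Timepoints: Weeks 1, 4, 13, and 26" in SAP Table 10 plans about 250 subjects for Cohort 2, roughly half of the 500 targeted. Cohort 2 is the only cohort that would be imputed.

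**The case against.** The code is labelled as a sample, and table specifications sit in a separate document that may define the imputation output. SAP 4.1 says Part A tables are shown by arm. SAP 4.1.2 presents the imputation as a check on the primary endpoint, so an arm comparison may be implied and merely under-specified. That is a fair reading of the analysis step. It does not rescue the imputation model, because the text of 4.2.3.1 omits arm as plainly as the code does. Arm-wise unadjusted GMTs with 95% limits would still not give the adjusted ratio or its 97.5% bound.

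The error rates are also hypothetical. They describe a ratio the plan does not ask for, at a true value exactly on the margin, in an analysis that makes no confirmatory claim. They are not the trial's type I error. The 10% figure is a planning allowance for dropouts and invalid samples. The imputation uses the Safety Analysis Set and keeps out-of-window results, so the real missing fraction may be lower, and near the 5% trigger the inflation is small. All of this stands and limits the weight of the point.

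A 95% interval is not foreign to the plan either, since SAP 4.2.2 reports both 95% and 97.5% intervals. What is missing is the 97.5% bound for an arm contrast. SAP 4.2.3 has two other sensitivity analyses, one on the Safety Analysis Set and one excluding subjects by nucleocapsid result, but neither imputes missing Week 2 values.

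**Conclusion.** The point holds and should be fixed. It follows from the text and code alone: arm is absent from the imputation model, and the only stated analysis step pools both arms into one GMT with 95% limits. Run as written, the check says nothing about the Cohort 2 ratio.

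The size of any later bias is illustrative. Near the trigger, at 6% missing with no Week 1 data, a true ratio of 0.67 reads about 0.687 with error 0.014 to 0.018. At 10% missing it reads about 0.69 to 0.70 with error about 0.015 to 0.023, against a nominal 0.0125. These figures rest on the missingness and correlation assumptions above. There is no bias at a ratio of 1, and above 1 the ratio is pulled down, against ABNCoV2. The primary analysis is untouched.

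**What to change.** In SAP 4.2.3.1 and Appendix 2:

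- Add vaccination arm to the imputation predictors, or impute separately by arm.
- Add `ltiterW2` to the VAR statement. It is the variable being imputed and is not listed.
- Fit the SAP 4.2.2 model (arm, age, log10 baseline) in each completed dataset in place of `PROC MEANS`.
- Pool the arm difference in `PROC MIANALYZE` with alpha = 0.025, back-transform it to a GMT ratio, and compare the 97.5% lower bound with 0.67.
- Tidy the code: the KEEP statement drops the back-transformed limits (`GMT_LCL`, `GMT_UCL`), and the output datasets are named for Cohort 1, which gets no imputation.

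The cost is a few lines of text and code, with no new data and no effect on the timeline.

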#### 4.2.4. Supplementary Analyses

There are no supplementary analyses.

#### 4.2.5. Subgroup Analyses

The primary analysis (and similar secondary and exploratory time points listed below) will also be performed and summarized by subgroups for Part A. Subgroups will include:

- Age Group (<65 years and ≥65 years)
- Prior Vaccination Regimen (as randomized groupings)

Cohort 1:

- 2 doses of mRNA vaccine,
- 1 dose or 2 doses of adenovirus-based vaccine,
- 1 dose of adenovirus-based vaccine followed within 3 months by 1 dose of mRNA vaccine,
- Other authorized primary vaccination regimen.

Cohort 2:

- 2 doses of mRNA primary vaccines plus 1 booster dose of mRNA vaccine,
- 1 dose or 2 doses of adenovirus-based primary vaccines plus 1 booster dose of mRNA vaccine,
- Other authorized primary vaccination and boost vaccination combinations.
- Prior Vaccination Regimen (as derived from COVID-19 history data, same categories as above if it is determined that >5% are different from randomized)
- Baseline Neutralizing Antibody Result (< LLOQ, ≥ LLOQ to < median, ≥ median)
  - Median is calculated from the corresponding trial part and cohort values ≥ LLOQ
- Time from Previous Vaccination (time from the most recent COVID-19 vaccination to the trial vaccination)
  - Time is calculated in months as (date of trial vaccination – date of most recent vaccination + 1)/30.4375
  - Times are categorized based on the median within part and cohort
- History of SARS-CoV-2 Infection (Yes vs. No)
- Baseline Comorbidity (Yes vs. No, see Section 4.1.6 for definition)

#### 4.2.6. Supportive Analyses of the Primary Endpoint

The primary analysis will be supported by descriptive summaries (GMT, 95% CI, and median) for each time point (pre- and post-vaccination). Descriptive summaries will be presented for Part A Cohorts 1 and 2 separately and combined.

The proportion of subjects with  $\geq 2$ -fold and  $\geq 4$ -fold increase in neutralizing antibody results to the SARS-CoV-2 index virus from baseline to 2 weeks post-trial vaccination will be summarized using frequencies and percentages along with exact Clopper-Pearson 95% CIs within vaccination arm in each cohort. In addition, a similar summary table as a sensitivity analysis using the Safety Analysis Set will also be presented. Subjects missing a value for a time point who did not achieve a response at a previous time point are counted as non-responders for this sensitivity analysis.

### **4.3. Secondary Estimand Analysis**

#### **4.3.1. Key Secondary Estimands**

The key secondary variables of interest are the subjects' neutralizing antibody results against circulating SARS-CoV-2 VOCs measured at Week 2 in Part A Cohorts 1 and 2, and they will be summarized as the ratios of GMTs for ABNCoV2 compared to Comirnaty.

The null hypothesis of inferiority will be rejected if the ratio of GMTs against the SARS-CoV-2 VOCs, for ABNCoV2 vaccine compared to Comirnaty vaccine, is within the non-inferiority margin of 0.67. Only Part A cohort(s) that meet the primary success criterion will be formally tested sequentially for non-inferiority of ABNCoV2 to Comirnaty for each VOC, and a Bonferroni correction will be used to control the overall type I error rate for the trial. Details are provided in Section 2.1.

The intercurrent events for the secondary analyses are the same as for the primary analysis and will be handled in a similar fashion described in Section 4.2.1.

##### **4.3.1.1. Definition of Endpoint(s)**

The definitions of the primary estimands apply to the secondary estimands.

##### **4.3.1.2. Main Analytical Approach**

The VOCs for Part A will be analyzed using the same analysis methods as those for the primary estimand described above. The precision of the CIs will be adjusted based on the number VOCs included in the key secondary analyses. The decision regarding which VOCs to include will be finalized before sample analysis begins. The GMT ratios and CIs with coverage adjusted for the non-inferiority hypothesis testing will also be calculated.

If the non-inferiority success criterion is met for a VOC (lower bound of the adjusted CI is  $\geq 0.67$ ), the p-value from the same model will be reported to assess superiority.

Analyses of other VOCs may also be performed similarly but not subjected to formal testing; such comparisons thus will not affect the trial-wide type I error.

##### **4.3.1.3. Sensitivity Analyses**

All results excluded from the secondary estimand analyses will be included with the sensitivity analysis for a full account of the trial population, i.e., the safety analysis set. Reasons for exclusion may include, but are not limited to:

- Intercurrent events indicative of SARS-CoV-2 infection prior to 2 weeks after vaccination

- A protocol deviation substantially affecting the immunogenicity outcome (i.e., exclusion from the Immunogenicity Analysis Set)

Another sensitive analysis will further exclude subjects who have significant fold increase in nucleocapsid protein antibody results although neither have positive PCR nor SARS-CoV-2 infection reported as an adverse event.

#### 4.3.1.4. Supplementary Analyses

There are no supplementary analyses.

#### 4.3.1.5. Subgroup Analyses

For each VOC, the same subgroup analyses as the primary estimand analysis in Section 4.2.5 will be presented for Part A.

#### 4.3.2. Other Secondary Endpoint Analyses

The other secondary endpoints of interest are the GMTs of neutralizing antibodies against the SARS-CoV-2 index virus at 2 weeks after trial vaccination in subjects receiving ABNCoV2 in the immunogenicity subsets of Part B Cohort 1 and Cohort 2.

The geometric mean, 95 % CI, median, minimum, and maximum of SARS-CoV-2 neutralizing antibody results for Part B will be calculated within each cohort at each of the 2 time points. Figures of neutralizing antibody results with GMT and fold increase will be plotted for the individual cohorts and combined. No sensitivity analyses will be performed for Part B subjects; however, the following subgroup analyses will be presented. Note, as prior vaccination regimen was not a randomization factor, it will be derived for the Part B neutralizing antibody analysis.

- Age Group (<65 years and ≥65 years)
- Prior Vaccination Regimen (as derived from COVID-19 history data)

Cohort 1:

- 2 doses of mRNA vaccine,
- 1 dose or 2 doses of adenovirus-based vaccine,
- 1 dose of adenovirus-based vaccine followed within 3 months by 1 dose of mRNA vaccine,
- Other authorized primary vaccination regimen.

Cohort 2:

- 2 doses of mRNA primary vaccines plus 1 booster dose of mRNA vaccine,
  - 1 dose or 2 doses of adenovirus-based primary vaccines plus 1 booster dose of mRNA vaccine,
  - Other authorized primary vaccination and boost vaccination combinations.
- Baseline Neutralizing Antibody Result (< LLOQ, ≥ LLOQ to < median, ≥ median)

- Median is calculated from the corresponding trial part and cohort values  $\geq$  LLOQ
- Time from Previous Vaccination (time from the most recent COVID-19 vaccination to the trial vaccination)
  - Time is calculated in months as (date of trial vaccination – date of most recent vaccination + 1)/30.4375
  - Times are categorized based on the median within part and cohort
- History of SARS-CoV-2 Infection (Yes vs. No)
- Baseline Comorbidity (Yes vs. No, see Section 4.1.6 for definition)

Descriptive analyses will be performed for each cohort similar to those described above, as well summaries for Cohort 1+2 combined. Comparisons will not be made for Part B as it has a single arm and is open label.

